### Base rate = 1 visit/year

[figure not shown]
### Base rate = 2 visits/year

[figure not shown]
### Base rate = 3 visits/year

[figure not shown]
### Base rate = 4 visits/year

### Base rate = 5 visits/year

For Aim 4, the sample of caregivers is expected to have a size of 675. From Powell et al., the estimated Bakas Caregiving Outcome Scale (BCOS) was 56.6 (SD=12.8) in the RDP group and 58.9 (10.7) in the RTP group. If we assume an attrition of 10% and 20%, we would have samples of 607 and 540 respectively. Assuming significance level of 0.05, power of 80%, SD=13 for both groups (based on the higher SD in Powell et al.), and a t-test (two-tailed), we calculated the power to find a change from 56 in RDP group to 59 - 70 in the RTP group, corresponding to about 5% to 20% increase in the BCOS (effect sizes of 0.23 to 1.08). The power was at least 80% (and mostly close to 100%) for all possible combinations of sample and effect sizes, except for the single circumstance of a very large attrition (n=540) and a low effect size (0.23), when the power was 0.76 (see graph below). Therefore, we will have enough power to test differences of at least 3 points in the BCOS.

For the Zarit Burden Interview, we can use the published data to estimate a possible standard deviation and given our expected sample size, we have 80% power to detect approximately a 1.14 difference if one exists. This is based on data from a study conducted on caregivers of Veterans with TBI who are broadly similar to our population with an average score of 15 and standard deviation of 10 on the 12 item Zarit Burden Interview. An assumption was made of equal sample sizes between the two groups which, with 80% power, alpha of .05, would require a .23 effect size to detect a difference between the two groups at 6-month post-injury. As with the Zarit Burden Questionnaire, there are no prior studies which allow us to precisely estimate power to detect a difference between groups. No prior research has been conducted with the final two caregiver measures to provide data to conduct power calculations.

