- Change in Bakas Caregiving Outcome Scale (BCOS) from 56 in SDC group to at least 59 in the OTC group, corresponding to at least 5% increase in the BCOS (effect sizes of 0.25 or more).

At the moment we have 142 caregivers and if we continue to enroll in the same rate, we will have about 471 caregivers by the end of the study. For that sample size, except when the effect size is smaller than 0.3, we will be able to detect a change in BCOS. If the effect size is larger, we will be able to detect it with 80% power even for smaller sample sizes (350 for an effect of at least 0.3, 275 for an effect of at least 0.35, and 250 for an effect of at least 0.4). For the smallest effect size of 0.25, we would need to have about 500 caregivers for a power of 80% to find that small difference. Given our current estimates of the total sample size for the caregivers, we are likely to have power to find a difference, if the difference exists.

---

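### The Aim 4 power statements for the Bakas scale are too favourable: 3 points is only 67–71% powered at the caregiver numbers now expected, its effect size is mislabelled 0.25, and the cited 2.3-point difference is never evaluated

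*Combined protocol and SAP*

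**What the plan says.** The Aim 4 paragraph of Power for Secondary Outcomes takes its planning data from a previous caregiver trial. It assigns that trial's arms to its own labels: the BCOS mean "was 56.6 (SD=12.8) in the RDP group and 58.9 (10.7) in the RTP group". It then sets "SD=13 for both groups", a two-tailed t-test and a significance level of 0.05, and says "we calculated the power to find a change from 56 in RDP group to 59 - 70 in the RTP group", giving "effect sizes of 0.23 to 1.08". From an expected 675 caregivers it derives 607 after 10% attrition and 540 after 20%. It reports at least 80% power for every combination except 540 with effect size 0.23, where power is 0.76. It concludes that power is enough for differences of 3 points or more.

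Power Analysis Revisited (January 28, 2019) keeps SD 13 and a change "from 56 in SDC group to at least 59 in the OTC group", but labels this an effect size of 0.25 or more. It projects about 471 caregivers at study end and says that effects below 0.3 are the exception to what can be detected at that size. It says about 500 caregivers would be needed for 0.25. It nevertheless closes that "we are likely to have power to find a difference, if the difference exists".

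Table 1 (Recruitment/Enrollment Assessment Timeline) now targets 540 caregivers enrolled. The milestone schedule in Appendix 1 counts 432 as complete caregiver follow-up at each time point, including 6 months, the time point of Hypothesis 4a.

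**The concern.** Three things do not fit together. First, the two reassuring conclusions rest on caregiver numbers or an effect-size label that the rest of the document does not support. Second, the 2019 section contradicts itself: a 3-point change at SD 13 lies below its own 0.3 threshold, so its caveat at 471 excludes the very change on which its calculation is built. Third, both sections cite or rely on a trial whose arms differed by 58.9 − 56.6 = 2.3 points, yet the smallest difference evaluated is 3.0, which is 3.0/2.3 = 1.30 times as large. The only description of the 3-point floor is that it is about a 5% increase; no statement says why a smaller change would not matter.

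What is at stake is how a non-significant BCOS result is read. Beside a claim of adequate power, it would tend to be taken as evidence of no caregiver benefit, although the trial would have a substantial chance of missing both the 3-point target and the cited 2.3-point difference.

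**Working it through.** **Inputs.** SD 13, two-sided alpha 0.05 and the two-sample t-test come from the Aim 4 paragraph. Equal arms are assumed, since patients are randomized 1:1. Total N: 675, 607 and 540 (Aim 4 paragraph), 471 (2019 update), 432 (Appendix 1). Each N is treated as the number analysed.

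**Method.** d = difference/SD. Power comes from the noncentral t with N − 2 degrees of freedom and noncentrality d√N/2. The normal approximation Φ(d√N/2 − 1.96) agrees within 0.002.

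**Reproducing the plan.** 3/13 = 0.2308.
- N = 540: 0.2308 × 23.24/2 = 2.68; Φ(2.68 − 1.96) = 0.765; noncentral t 0.763. The plan states 0.76.
- N = 607: 0.2308 × 24.64/2 = 2.84; Φ(0.88) = 0.811; noncentral t 0.810. The plan states at least 80%.
- Upper end of the grid: (70 − 56)/13 = 1.08, as stated.

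The method and the plan's figures are confirmed.

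**Power at each caregiver number (noncentral t).** The pooled cited SD is √((12.8² + 10.7²)/2) = 11.8, so d for 2.3 points is 2.3/13 = 0.177 or 2.3/11.8 = 0.195.

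| Total N | 3 points, SD 13 | 2.3 points, SD 13 | 2.3 points, SD 11.8 |
|---|---|---|---|
| 675 | 85% | 63% | 72% |
| 607 | 81% | 59% | 67% |
| 540 | 76% | 54% | 62% |
| 471 | 71% | 48% | 56% |
| 432 | 67% | 45% | 52% |

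**The 0.25 label.** An effect size of 0.25 at SD 13 is 0.25 × 13 = 3.25 points, not 3. Total N for 80% power is 4(1.960 + 0.842)²/d² = 31.4/d².
- d = 0.25: 31.4/0.0625 = 502, about 505 with the t distribution. This matches the update's figure of about 500.
- d = 0.2308: 31.4/0.05325 = 590, about 592 with the t distribution. This is the number for 56 versus 59.

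**Difference detectable with 80% power at SD 13**, approximately 13 × 2 × 2.80/√N: 3.0 points at 607, 3.1 at 540, 3.4 at 471, 3.5 at 432.

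**Precision.** The standard error of the difference is 2 × 13/√N. At 432 it is 26/20.78 = 1.25, so the 95% confidence interval extends about 1.96 × 1.25 = 2.5 points either side. Even an observed difference of zero would not exclude 2.3 points.

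**The case against.** The strongest reply is that the plan made no calculation error. The 0.76 and the 80% or more are right for the effect named; the effect range is stated openly; and the Aim 4 paragraph limits its conclusion to 3 points or more. All of that stands. A reader might infer from the 2.3-point citation that the stated power figures are arithmetically wrong, or that the plan was obliged to power on 2.3. The documents support neither. The plan attributes only the SD explicitly to the prior trial, and choosing a target other than one trial's point estimate is legitimate. The title of that trial in the reference list describes telehealth caregiver self-management, which is not the same intervention as the transition plan. What remains is that no rationale for 3 points is given and the only cited difference is left unevaluated.

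It is also true that the 2019 update discloses a limit at 471 caregivers, and that the General approach paragraph of the Data Analysis Plan promises cautious interpretation of non-primary outcomes with attention to effect sizes. These reduce the harm. They do not repair the closing sentence of the update, which its own caveat contradicts, nor the mislabelled effect size. Neither Aim 4 power section nor the General approach commits to a confidence interval for BCOS.

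Finally, Version 15.0 is dated after the October 2022 milestone for completing 12-month follow-up, so restating prospective power changes nothing in conduct. That is fair; the benefit now lies in how the result is reported.

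**Conclusion.** The concern holds as a minor point about overstated BCOS power. For the plan's own 3-point change at SD 13, power is 71% at 471 and 67% at 432, so neither the claim of enough power for 3 points nor the closing sentence of the 2019 update is supported at the numbers now expected. The 0.25 label should be 0.23, which raises the caregivers needed for 80% power from about 500 to about 592. At the cited 2.3 points, power is 54–59% at 540–607 with SD 13 (62–67% with the cited SDs pooled), 63% or 72% at 675, and 45–48% at 432–471 with SD 13.

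This rests on equal caregiver arms, a two-sided t-test at 0.05, and reading 471 and 432 as numbers analysed. If 471 means caregivers enrolled, before attrition, power is lower. It does not show that the trial is underpowered overall: BCOS is one of several secondary caregiver measures, and power for the patient primary outcomes is a separate calculation.

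**What to change.** In the two Aim 4 power paragraphs:
- Correct the effect size for 56 versus 59 from 0.25 to 0.23, and the number needed for 80% power from about 500 to about 592.
- Replace the two conclusions of adequate power with the BCOS difference detectable with 80% power at the number analysed: about 3.4 points at 471 and 3.5 at 432, with SD 13.
- Add the cited 2.3-point difference as a sensitivity row with its power, and either give a reason for the 3-point floor or say that it was a working choice.

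In the Aim 4 analysis text, state that the BCOS difference will be reported with its 95% confidence interval and that a non-significant result will not be read as excluding 2.3 points.

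The cost is a few sentences and a less favourable stated power for a secondary outcome. No change in enrolment, data collection or test is needed.

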Zarit Burden Interview: The Zarit Burden Interview was initially developed for caregivers of individuals with dementia. Short forms have been developed, and the 12 item version addresses the concerns that our stakeholders feel are most important and that we feel are most relevant to our study interventions. The Zarit Burden Interview has been used previously in studies on caregivers of individuals with TBI. We hypothesize that caregivers for participants randomized into the RTP arm of the study will report lower burden compared to those caregivers of participants randomized into the RDP arm.

Prior research with this scale has been primarily descriptive and did not exactly match the timeline (within one year of TBI) nor injury severity of our study population. We can use the published data to estimate a possible standard deviation and given our expected sample size, we have 80% power to detect approximately a 2.29 difference if one exists. This is based on data from a study conducted on caregivers of Veterans with TBI who are broadly similar to our population with an average score of 15 and standard deviation of 10 on the 12 item Zarit Burden Interview. An assumption was made of equal sample sizes between the two groups which, with 80% power, alpha of .05, would require a .229 effect size to detect a difference between the two groups at 6 months post injury.

SF-12: The SF-12 is a measure of health-related quality of life (HRQOL) and allows for 2 component scores to be determined: physical health and mental health. The SF-12 has been used in examining HRQOL in caregiver populations for other disorders, but not as frequently assessed in caregivers of individuals with TBI. However, the 36-item version has been found to show change over time in caregivers of persons with TBI. We hypothesize that caregivers for participants enrolled in the RTP arm of the study will report better HRQOL in both physical and mental health domains compared to those caregivers of participants enrolled in RDP alone.

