### **Power for Secondary Outcomes:**

For Aim 3, under the assumptions that our SDC group would have a proportion of 0.79 of people going to more than 75% of their scheduled visits, we calculated the size of change in the proportion of people receiving 75%+ visits in the OTC group that we would be able to detect with a significance level of 0.05 (two-tailed proportion test), power of 0.80, and varying the sample size from 100 to 900.

With 80% power, we would be able to statistically detect a proportion in the OTC group of 0.91 with a sample of 300 individuals, 0.88 with a sample size of 500, and of 0.86 with 900 (see graph below).

[figure not shown]
[figure not shown]
We will also test differences in number of hospitalizations, number of emergency department visits, and number of unplanned outpatient visits per year. These outcomes will be compared using a Poisson model. For the power analysis, we adjusted the significance level to 0.017 after using Bonferroni adjustment (0.05/3), and we considered sample sizes of 300, 500, 700, and 900. We considered the base rates of 1-4 events per year for the SDC group and calculated the power of detecting a decrease in that rate from 10% to 50% in the OTC group. Using G\*Power and the specifications above, the summary of the findings are as follows:

- The higher the base rate for the SDC group, the higher the power to find a difference;
- Power is at least 80% to find a decrease of 20% in the number of events, except when the base rate is 1, in which case the decrease would need to be 22-25% to be detected;
- Attrition or low enrollment (represented by sample sizes of 300, 500 and 700) have an effect but might be important only for a small base rate (such as 1 visit/year) and sample size 300 (unlikely to happen);
- Power for secondary analysis will be high to find a decrease of 20% in mean number of events (equivalent to odds ratio of .8 when comparing the OTC to the SDC group), except for sample lower than 500 (which is unlikely to happen).

The graphs below show the power for each base rate (odds ratio in x-axis and power in the y-axis).

[figure not shown]
[figure not shown]
Base rate = 1

Base rate = 2

[figure not shown]
Base rate = 3

Base Rate = 4

For Aim 4, for caregiver outcome, we assumed the following parameters:

- Sample sizes from 250 to 600 (by 50);
- Significance level of 0.05,
- SD=13 for both groups (based on the higher SD in Powell et al.),
- T-test (two-tailed)

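### Aim 4 caregiver power is overstated: the 1.14-point Zarit difference is half what its own inputs give, and 3 Bakas points does not reach 80% power at 540 or at the 432 now expected

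*Combined protocol and SAP*

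**What the plan says.** **Zarit.** The Aim 4 text under Power for Secondary Outcomes states that "given our expected sample size, we have 80% power to detect approximately a 1.14 difference if one exists". Its inputs are a "standard deviation of 10 on the 12 item Zarit Burden Interview", equal groups, alpha 0.05 and 80% power, which it says "would require a .23 effect size to detect a difference between the two groups at 6-month post-injury". The Zarit paragraph under Secondary Outcomes uses the same source, SD, alpha and power, with an effect size of 0.229, and states that "we have 80% power to detect approximately a 2.29 difference if one exists".

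**Bakas (BCOS), main power section.** The smallest difference considered is 56 v 59, at SD 13. The range of differences is described as "corresponding to about 5% to 20% increase in the BCOS (effect sizes of 0.23 to 1.08"). Power is put at 80% or more except for "a very large attrition (n=540) and a low effect size (0.23), when the power was 0.76". The conclusion is: "Therefore, we will have enough power to test differences of at least 3 points in the BCOS". Here 540 is what remains of 675 after 20% attrition.

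**Bakas, January 2019 revisit.** This keeps "SD=13 for both groups" but labels 56 v 59 as an effect of 0.25 or more. It projects 471 enrolled caregivers, excepts effects below 0.3 from its claim at that size, and says about 500 are needed for an effect of 0.25. It contains no Zarit calculation.

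**Current numbers.** Table 1 (Recruitment/Enrollment Assessment Timeline) and the Milestone Schedule in Appendix 1 set caregiver enrolment at 540. The Milestone Schedule expects 432 at the 6-month follow-up. Table 1 gives 110 lost, which leaves 430.

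**The concern.** The document holds two incompatible detectable differences for one Zarit calculation, and the one in the power section cannot come from the inputs printed beside it. The Bakas conclusion does not follow from the power figure in the sentence before it. The 540 that was the heavy-attrition case is now the enrolment target, so the plan's former worst case is better than its present expectation.

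What is at stake is how a null result under Hypothesis 4a would be read. A reader relying on the power section would think the trial could detect a Zarit difference half as large as it can, and that it had at least 80% power for 3 Bakas points. The point concerns the 6-month t-tests only, not the longitudinal models of Hypothesis 4b.

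**Working it through.** **Method.** Two-sample t-test, two-sided alpha 0.05, equal arms, noncentral t. As a check, the normal approximation for the detectable difference with total N is SD × (1.960 + 0.842) × 2/√N.

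**1. Figures that reproduce.**
- Bakas, N = 540, d = 0.23: power 0.76, as stated.
- Zarit, N = 600, SD 10: 10 × 2.802 × 2/√600 = 2.29, as in Secondary Outcomes.
- d = 0.25: N = 506, consistent with about 500 in the 2019 revisit.

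**2. The figure that does not.** From the paragraph's own inputs, 0.23 × 10 = 2.3 points, not 1.14. None of the caregiver numbers in the table below gives 1.14. It appears only if the SD is about 5, or if a one-sample formula is used (10 × 2.802/√600 = 1.14). Neither fits a two-group comparison with SD 10. It is also half of 2.28, the value at N = 607.

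**3. Across the caregiver numbers.** The Bakas effect is 3/13 = 0.231.

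| Caregivers analysed | Detectable d, 80% power | Zarit points (SD 10) | Power, 3 Bakas points (SD 13) |
|---|---|---|---|
| 675 | 0.216 | 2.16 | 0.85 |
| 607 | 0.228 | 2.28 | 0.81 |
| 600 | 0.229 | 2.29 | 0.81 |
| 540 | 0.242 | 2.42 | 0.76 |
| 471 | 0.259 | 2.59 | 0.71 |
| 432 (540 × 0.8) | 0.270 | 2.70 | 0.67 |
| 430 (540 − 110) | 0.271 | 2.71 | 0.67 |
| 377 (471 × 0.8) | 0.289 | 2.89 | 0.61 |

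**4. Zarit, 1.14 points.** d = 1.14/10 = 0.114. Power is 0.29 at 600 and 0.22 at 432. Reaching 80% needs about 2,418 caregivers.

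**5. Bakas, 3 points.**
- With SD 13, 80% power needs 592 analysed caregivers. At 432 the detectable difference is 0.270 × 13 = 3.5 points.
- With the arm SDs the protocol cites (12.8 and 10.7), the pooled SD is √((12.8² + 10.7²)/2) = 11.80 and d = 3/11.80 = 0.254. Power is 0.84 at 540, 0.75 at 432 and 0.69 at 377. N for 80% is 488, and the detectable difference at 432 is 3.2 points.

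**6. The 2019 revisit.** With its own SD of 13, 56 v 59 is d = 0.23, so its figure of about 500 does not apply to that difference. For d = 0.30, N for 80% is 352. Power is 0.875 at 432 and 0.83 at 377, so its claim for effects of 0.3 or more survives attrition.

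**The case against.** The Zarit error exposes itself: the right inputs stand in the same paragraph and the right answer in Secondary Outcomes. The 0.76 for the Bakas is disclosed, and the conclusion after it is true at 675 and 607. The 2019 revisit then excepts effects below 0.3, which covers a 3-point difference, so the later text does not claim 80% power for it. SD 13 is deliberately conservative; with the cited arm SDs, 3 points has 0.84 power at 540. The 377 combines a January 2019 projection with an 80% retention mark that the revision history dates to October 2019. Aim 4 is secondary, recruitment was scheduled to end on 10/31/2021, none of the planned tests uses these figures, and the analysis plan already promises caution on non-primary outcomes.

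Most of this stands as a limit on weight. It does not remove the errors. The 1.14 is uncorrected in the current version. The 2019 exception does not withdraw the earlier Bakas sentence, and power for 3 points at 432 is below 80% under either SD choice. The 377 is an illustration rather than a plan figure, although a 20% attrition scenario was already in the main power section; the conclusion at 432 does not depend on it.

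**Conclusion.** The concern holds. The Zarit figure of 1.14 is wrong by a factor of two against its own inputs. The unqualified Bakas conclusion fails the plan's 80% standard at its own 540 (0.76) and at the 432 now expected (0.67 at SD 13, 0.75 at the cited arm SDs). In the 2019 revisit, the 0.25 label should be 0.23 and the 471 is before attrition; its figure of about 500 for d = 0.25 and its claim for effects of 0.3 or more are sound.

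This rests on a two-sided 0.05 t-test, equal arms and the documents' SDs. The Zarit values in points also assume the 12-item form. The consequence is limited to the stated sensitivity of a secondary aim; the primary outcome and the planned analyses are unaffected.

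**What to change.** 1. **Zarit.** Delete 1.14. In both Secondary Outcomes and the power section, give one detectable effect at 432 retained caregivers: d = 0.27. This is 2.7 points only if the 12-item form (SD 10) is the one administered. The caregiver questionnaire list under Follow Up Data Collection describes a 22-item form, so reconcile the two before quoting points.
2. **Bakas, main power section.** Replace the concluding sentence, or attach a dated note, with: at 432 retained caregivers, power is 0.67 for 3 points and 80% for about 3.5 points (SD 13); with the cited arm SDs, power for 3 points is 0.75.
3. **January 2019 revisit.** By correction or dated note, change the label for 56 v 59 from 0.25 to 0.23. Keep about 500 for d = 0.25, and add that 3 points needs about 592 analysed caregivers. State that 471 is before attrition (about 377 after 20% loss, with power 0.61 for 3 points and 0.83 for d = 0.30). Keep the closing sentence, repeating in it the exception for effects below 0.3. A dated note would leave the 2019 record intact.

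The cost is wording only: no extra caregivers and no change to any analysis. The stated power for a secondary aim becomes less favourable.

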### **Power Analysis Revisited by [name]., Study Biostatistician, January 28, 2019**

Power Analysis for primary outcome:

[figure not shown]
The following reproduces the power analysis performed in the original proposal, except that it extends the range of sample size from 100 to 900 (by 100) and that we looked at smaller effect sizes (starting at 0.3 instead of 0.5). The specific parameters used in the calculations are as follows:

Test: t-test for independent samples, two-tailed, allocation ratio=1

Significance level=0.05

Mean PART-O scores (Intervention mean minus control mean): Effect sizes of 0.3 to 0.75 by increments of 0.05.

Sample sizes: from 100 to 900 individuals (by 100)

[figure not shown]

For the primary outcome, even a small sample size of 300 will have 0.80 power to detect a small effect size of 0.3. Therefore, it is unlikely that we would not find a difference between the two groups if the difference exists.

